### 3.2 Efficacy Endpoints

The primary efficacy endpoints are:

- Time to sustained resolution of COVID-19 signs and symptoms (in all subjects) as measured by the time from baseline (in hours) when cough, sore throat, nasal congestion, headache, chills and or sweats, myalgia, fatigue, and nausea (with or without vomiting) have been assessed by the subject as none (0) or mild (1) and all symptoms remain at or below 1 until the Day 14 visit. Subjects reporting a persistent fever (100.5 degrees for 36 hours or more) and/or SpO2 levels <96% with any shortness of breath are considered not to have met the success criterion on that day even if all other symptoms are reported as none (0) or mild (1).
- Time to sustained resolution of COVID-19 signs and symptoms (in subjects with mild disease at baseline) as measured by the time from baseline (in hours) when cough, sore throat, nasal congestion, headache, chills and or sweats, myalgia, fatigue, and nausea (with or without vomiting) have been assessed by the subject as none (0) or mild (1) and all symptoms remain at or below 1 until the Day 14 visit. Subjects reporting a persistent fever (100.5 degrees for 36 hours or more) and/or SpO2 levels <96% with any shortness of breath are considered not to have met the success criterion on that day even if all other symptoms are reported as none (0) or mild (1).

Note: The second primary endpoint is defined in the same way as the first primary endpoint, but is evaluated only in subjects with mild disease at baseline.

Secondary clinical endpoints:

- Proportion of study subjects who achieve 'Composite Resolution' at Day 8 defined as both a negative SARS-CoV-2 antigen test within the window for Visit 4 (Days 7 – 9) and all eight symptoms assessed by the subject as none (0) or mild (1), absence of fever and SpO2  $\geq 96\%$  without shortness of breath at study day 8 (as reported on the Diary Card Day 8-Assessment 1).
- Proportion of study subjects who experience progression of COVID-19 as defined by an increase of the composite COVID-19 severity score greater than baseline at any point in the study on or after Day 3.
- Proportion of study subjects who answer yes to either of the following patient-reported global impression assessments independently at each of the Day 8 and Day 14 visits,
  - a) In the past 24 hours, have you returned to your usual health (before your COVID-19 illness)?

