### 3.3 Sample Size Determination

The target number of subjects to be randomized per cohort is 30 individuals seronegative for SARS-CoV-2 Spike IgG antibodies (20 subjects to the RD-X19 treatment arm and 10 subjects for Sham control), for a minimum total of 60 subjects. At the sponsors option, the total number of subjects can be increased by an additional 150 total subjects to include all serostatuses after a dose has been selected based on adequate safety/tolerability observed for the final dose cohort.

Based on findings in the EB-P12-01, the hazard ratio observed for the time to sustained symptom resolution in that early feasibility trial was HR=0.4 between active RD-X19 and Sham.

The increased sample size in the Final Cohort (up to 180 total), with an anticipated roughly equal number of antibody positive to negative individuals enrolled during the option, will lead to approximately 90 seropositive and 90 seronegative subjects. The modified Full Analysis Set (mFAS) population containing only antibody negative subjects (as defined in Section 4, 60 RD-X19: 30 Sham) has at least 90% power to detect meaningful changes in SARS-CoV-2 symptom resolution from baseline (Hazard ratio of 0.4) for the first primary endpoint. These power calculations assume that testing will be carried out using  $\alpha = 0.025$  one-sided, up to a 20% dropout rate due to discontinuations or hospitalizations, as well as an assumption that the proportions of subjects having the event (for the first primary endpoint) by Day 14 is 85% for the RD-X19 arm and 75% for the Sham arm.

In the Full Analysis Set (FAS) for the Final Cohort, the primary analysis population including all randomized subjects receiving at least one treatment, the increased sample size (increase by a minimum of 100 RD-X19: 50 Sham) has at least 90% power to detect a Hazard ratio of 0.5 between RD-X19 and Sham for the first primary endpoint. These power calculations assume that testing will be carried out using  $\alpha = 0.025$  one-sided, as well as an assumption that the proportions of subjects having the event (for the first primary endpoint) by Day 14 is 90% for the RD-X19 arm and 85% for the Sham arm, with adjustment for multiple endpoints as described in Section 5.1.1.

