## 4 Populations To Be Analyzed

Three subject populations are defined as follows:

- (1) Safety/Full Analysis Set (FAS): This population will include all randomized subjects who receive at least 1 study treatment. This Population will be used for all analysis of safety data, and is also the primary analysis population for efficacy. Subjects will be analyzed based on actual treatment received.
- (2) Modified Full Analysis Set (mFAS): This population will include all randomized subjects who received at least one treatment and who tested negative for SARS-CoV-2 antibodies at baseline. Subjects will be analyzed based on actual treatment received.
- (3) Per-Protocol Population (PP): This population will include all randomized subjects in the FAS population who complete the study and did not have a major protocol deviation (MPD). The PP population will be used for supportive analysis of the clinical and virological endpoints. MPDs are those that could have interfered with the administration of treatment or the precise evaluation of treatment efficacy.

MPDs may include but will not be limited to the following:

- Violation of inclusion/exclusion criteria
- Use of prohibited concomitant medications during the treatment period
- Missed Visit 4 (Day 8) or Visit 4 outside of window
- Did not complete 100% (6 out of 6) of scheduled doses in the first 3 days, or at least 75% (11 out of 14), regardless of the time of enrollment on Day 1
- Returned for Day 14 Visit outside the designated visit window

All MPDs will be identified and documented in the Protocol Violation and Protocol Deviation Log before the database lock and study unblinding for analysis.

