- Scenario 3: For Day x (pm), if severity is missing for all 8 symptoms, the diary entries from the previous completed entry, either Day x (am) or Day x-1 (pm), will be carried forward for Day x (pm). For Day x (am), if severity is missing for all 8 symptoms, the diary entries from the previous completed entry, either Day x-1 (pm) or Day x-1 (am) will be carried forward for Day x (am). Same applied to fever and SpO2 level/shortness of breath.
- Scenario 4: For Day x assessment y where all 8 symptoms are scored 0 or 1, if fever or SpO2 level is missing, subject’s success or failure for Day x assessment y will be determined in the same way as in Scenario 2.

For derivation of the primary efficacy endpoints, subjects who were hospitalized due to COVID-19 will be designated as treatment failures, and right censored at 384 hours (16 days), i.e., censored at the end of the Visit 5 window.

For subjects who discontinued the study early for any reason other than hospitalization for COVID-19, only diary data up to subject’s discontinuation date will be used. For derivation of the primary efficacy endpoints such subjects will be considered censored at the time of their last assessment.

**Note:** Subjects discontinuing for any reason are ineligible to meet the success criteria on either primary efficacy endpoint because "success" requires the conditions to be met until the Day 14 visit.

The COVID-19 Composite Severity Score (CSS) at baseline is defined as the sum of the eight individual COVID-19 signs and symptoms severity scores divided by eight. For purposes of calculating the COVID-19 composite severity score in the secondary endpoint of worsening disease from baseline, subjects with missing diary card entries (reporting none of eight symptoms scored) will not be considered to have met the criteria for worsening of disease at that assessment timepoint. Subjects with incomplete diary card entries (reporting from 1 to 7 of the eight symptoms scored), will be handled by dividing the sum of all scores reported by the number of scores reported, and compared to the baseline CSS.

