### 5.5 Efficacy Analyses

The primary analysis population for all primary and secondary efficacy endpoints is the FAS population. Supportive analyses will be carried out on the mFAS and PP populations for the primary endpoints and for all secondary endpoints.

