Note: Sustained resolution of COVID-19 signs and symptoms is defined as all 8 signs and symptoms (cough, sore throat, nasal congestion, headache, chills and/or sweats, myalgia, fatigue, and nausea) have been assessed by the subject as none (0) or mild (1) and all remain at or below 1 until study Day 14. Subjects reporting a persistent fever (100.5 degrees for 36 hours or more) and/or SpO2 levels <96% with any shortness of breath are considered not to have met the success criterion on that day even if all other symptoms are reported as none (0) or mild (1). Subjects who were hospitalized due to COVID-19 are designated as treatment failures, and right censored at 384 hours (16 days). Subjects discontinued for other reasons are censored at their time of discontinuation. Other subjects who did not achieve sustained resolution at the last assessment of the study are considered censored at the time of the last assessment.

[1] Log-Rank Test and Cox PH Regression analyses were performed unstratified

[2] The Cox PH regression model included pre-specified covariates: COVID-19 Composite Severity Score at Baseline (<1.25,  $\geq 1.25$ ), Baseline Disease Status (mild, moderate), Sex (male, female), Age (<50,  $\geq 50$ ), Baseline Antibody Status (positive, negative). For mFAS, the Cox PH regression model does not include the covariate related to baseline antibody status.

Source: Listing 16.x.x

O:\Studies\EmitBio\EB-P20-01\Biometrics\Programs\Tables\xxx.sas ran on Month Day, Year at hh:mm on data from Month Day, Year.

Table 14.2.1.2 – Primary Analysis and Supportive Analyses of the Second Primary Efficacy Endpoint: Time (Hours) to Sustained Resolution of COVID-19 Signs and Symptoms in Subjects with Mild Disease at Baseline for the Final Cohort

Population	Statistics	Final Cohort RD-X19	Sham
Full Analysis Set (FAS) #			
N		XX	XX
n (%) Censored		XX (XX.X)	XX (XX.X)
Median of Time to Sustained Resolution (95% CI)		XX.X (XX.X, XX.X)	XX.X (XX.X, XX.X)
25 th Percentile of Time to Sustained Resolution (95% CI)		XX.X (XX.X, XX.X)	XX.X (XX.X, XX.X)
75 th Percentile of Time to Sustained Resolution (95% CI)		XX.X (XX.X, XX.X)	XX.X (XX.X, XX.X)
1-sided P-value for treatment comparison from Log-rank Test 		0.XXXX	
2-sided P-value for treatment comparison from Log-rank Test 		0.XXX	
Final Cohort RD-X19 to Final Cohort Sham Hazard Ratio 		X.XXX	
95% CI 		(X.XXX, X.XXX)	

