Note: Sustained resolution of COVID-19 signs and symptoms is defined as all 8 signs and symptoms (cough, sore throat, nasal congestion, headache, chills and/or sweats, myalgia, fatigue, and nausea) have been assessed by the subject as none (0) or mild (1) and all remain at or below 1 until study Day 14. Subjects reporting a persistent fever (100.5 degrees for 36 hours or more) and/or SpO2 levels <96% with any shortness of breath are considered not to have met the success criterion on that day even if all other symptoms are reported as none (0) or mild (1). Subjects who were hospitalized due to COVID-19 are designated as treatment failures, and right censored at 384 hours (16 days). Subjects discontinuing for other reasons are censored at their time of discontinuation. Other subjects who did not achieve sustained resolution at the last assessment of the study are considered censored at the time of the last assessment.

[1] Log-Rank Test and Cox PH Regression analyses were performed unstratified for RD-X19 from Cohort A vs. Pooled Sham, and stratified by cohort for Pooled RD-X19 vs. Pooled Sham.

[2] The Cox PH regression model included pre-specified covariates: COVID-19 Composite Severity Score at Baseline (<1.25,  $\geq$ 1.25)), Baseline Disease Status (mild, moderate), Sex (male, female), Age (<50,  $\geq$ 50), Baseline Antibody Status (positive, negative). For mFAS, the Cox PH regression model does not include the covariate related to baseline antibody status. Analyses were performed unstratified for RD-X19 from Cohort A vs. Pooled Sham, and stratified by cohort for Pooled RD-X19 vs. Pooled Sham.

Source: Listing 16.x.x

O:\Studies\EmitBio\EB-P20-01\Biometrics\Programs\Tables\xxx.sas ran on Month Day, Year at hh:mm on data from Month Day, Year.

Table 14.2.1.4 – Additional Supportive Analysis of the Second Primary Efficacy Endpoint: Time (Hours) to Sustained Resolution of COVID-19 Signs and Symptoms in Subjects with Mild Disease at Baseline, Both Cohorts Combined and RD-X19 from Cohort A

Population	Statistics	Pooled RD-X19	RD-X19 from Cohort A	Pooled Sham
Full Analysis Set (FAS)				
N		XX	XX	XX
n (%) Censored		XX (XX.X)	XX (XX.X)	XX (XX.X)
Median of Time to Sustained Resolution (95% CI)		XX.X (XX.X, XX.X)	XX.X (XX.X, XX.X)	XX.X (XX.X, XX.X)
25 th Percentile of Time to Sustained Resolution (95% CI)		XX.X (XX.X, XX.X)	XX.X (XX.X, XX.X)	XX.X (XX.X, XX.X)

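### Discontinuers who have already resolved stay at risk with no possible event; no FAS analysis tests this, and the stated mFAS power at up to 20% dropout does not allow for it

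*SAP*

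**What the plan says.** SAP 3.2 dates the primary event to the start of resolution, in hours, but counts it only if "all symptoms remain at or below 1 until the Day 14 visit". SAP 5.2.1 then deals with early leavers. Those not hospitalised for COVID-19 contribute diary data up to the day they leave, and "For derivation of the primary efficacy endpoints such subjects will be considered censored at the time of their last assessment". A Note adds: "Subjects discontinuing for any reason are ineligible to meet the success criteria on either primary efficacy endpoint", because success has to last to Day 14. Subjects hospitalised for COVID-19 are failures, censored at 384 hours.

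The primary analysis is the unstratified log-rank test in the FAS of the Final Cohort (SAP 5.5.1). For other populations, SAP 5.5 says: "Supportive analyses will be carried out on the mFAS and PP populations for the primary endpoints and for all secondary endpoints". The PP population is "all randomized subjects in the FAS population who complete the study and did not have a major protocol deviation" (SAP 4).

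SAP 3.3 gives the mFAS (60:30) at least 90% power for a hazard ratio of 0.4 at one-sided 0.025. It assumes event proportions of 85% and 75% by Day 14 and "up to a 20% dropout rate due to discontinuations or hospitalizations". The FAS power statement in the same section names no dropout rate.

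The table footnotes word the end of risk time differently: "Subjects discontinued for other reasons are censored at their time of discontinuation" (Tables 14.2.1.1 and 14.2.1.2) and "Subjects discontinuing for other reasons are censored at their time of discontinuation" (Tables 14.2.1.3 and 14.2.1.4).

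**The concern.** A log-rank test assumes that anyone in the risk set could still have the event. Take a subject who clears on Day 4, stays clear and leaves on Day 11. Under the rule this subject is counted as unresolved for seven further days (168 hours) and can never be an event. The censoring is informative by construction, even if people leave at random.

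No planned analysis isolates this. The mFAS uses the same derivation, and so do the single-term Cox, covariate-adjusted, pooled and low-dose analyses. The PP population drops discontinuers together with major deviators, so it mixes this question with missed doses and visit windows. At stake are the primary test and hazard ratio for both primary endpoints, and the mFAS power figure.

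**Working it through.** **1. The plan's own figure.** Expected events after 20% dropout: (60 × 0.85 + 30 × 0.75) × 0.8 = 58.8. Schoenfeld: z = √(58.8 × 2/3 × 1/3) × ln(1/0.4) − 1.96 = 3.615 × 0.916 − 1.96 = 1.35, so power is 91.2%. The statement reproduces, with dropout counted only as lost events and the hazard ratio left undiluted.

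**2. What the rule does to the hazard.** Let a share d of an arm discontinue, G(t) be the fraction of those still in the study at t, and S(t) the true unresolved fraction. Discontinuers never supply an event, so the apparent hazard is the true hazard multiplied by

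f = (1−d)S / [(1−d)S + dG].

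Below, benefit is written as a ratio above 1 (2.5 = 1/0.4, 2.0 = 1/0.5). Times are exponential and dropout is unrelated to outcome. These are assumptions, since the SAP gives no time distribution or dropout timing.

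- Equal dropout: mFAS, sham 75% by Day 14, ratio 2.5, d = 0.2, uniform timing, Day 7 (G = 0.5). Sham: S = 0.25^0.5 = 0.50, f = 0.4/0.5 = 0.80. RD-X19: S = 0.5^2.5 = 0.177, f = 0.141/0.241 = 0.586. Apparent ratio 2.5 × 0.586/0.80 = 1.83.
- Unequal dropout under the null: 85% resolved by Day 14 in both arms, so S = 0.15^0.5 = 0.387 at Day 7. With d = 0.1 on RD-X19, f = 0.875; with d = 0.2 on sham, f = 0.756. Apparent ratio 0.875/0.756 = 1.16 where the truth is 1.

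**3. Power under the SAP rule, by simulation.** There were 20,000 log-rank trials per cell, with equal dropout and nobody hospitalised. The SAP's 85% and 75% imply a ratio of ln(0.15)/ln(0.25) = 1.37 under proportional hazards, not 2.5, so only one rate can be held at a time. mFAS 60:30, sham held at 75%:

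| Dropout | Uniform days 0–14 | Last attended visit | Days 0–5 | Days 7–14 |
|---|---|---|---|---|
| none | 96.2% | 96.2% | 96.2% | 96.2% |
| 5% | 93.6% | 94.4% | 95.3% | 91.9% |
| 10% | 89.0% | 92.3% | 93.5% | 84.9% |
| 20% | 76.6% | 85.6% | 89.7% | 68.1% |

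With RD-X19 held at 85%, power is 92.1% with no dropout and 78.3/82.1/83.5/73.9% at 20% (same column order). If a quarter of the 20% are hospitalised and held to 384 hours, the sham-75% figure is 70% (uniform) or 76% (last visit). A non-proportional model that keeps both 85% and 75% gives 61–65% at 20% uniform.

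**4. How much is the rule itself.** Removing discontinuers from the risk set loses the same events without the dilution. At 20% that gives 91.3–91.6% with sham at 75%, so the rule costs about 15/6/2/23 points. With RD-X19 at 85% removal gives 84–85%. There the rule costs about 6/3/1/11 points, and the rest of the fall is lost events.

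**5. FAS, 120:60, ratio 2.0, sham 85%.** Schoenfeld with 120 × 0.9 + 60 × 0.85 = 159 events gives 98.5% with no dropout. Under the rule, simulated power is 96.5/97.3/98.0/94.7% at 5%, 92.7/96.0/97.0/88.0% at 10% and 80.0/91.1/94.5/69.6% at 20%. At 10% uniform dropout about 12 of 180 subjects leave while resolved; at 5%, about 6.

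**6. Type I error, null FAS, uniform timing, nominal 2.5%.**

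| Dropout, RD-X19 vs sham | Rejection rate |
|---|---|
| equal | 2.1–2.4% |
| 5% vs 10% | 5.0–5.5% |
| 10% vs 20% | 9.3–9.8% |
| 20% vs 10% | 0.3–0.4% |

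Leaving at the last attended visit softens these: 3.7%, 6.0% and 0.7% for the three unequal rows. The experimentwise error of the SAP's Hochberg procedure (174 subjects, 98 mild, uniform) is 4.4% at 5% vs 10%, 8.6% at 10% vs 20%, and 2.3% when dropout is equal.

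**7. The alternative rule.** Counting a resolved discontinuer as an event at the start of the run gives 2.0–2.4% error without relapse, for equal and unequal dropout. That does not hold if relapse is common and a single clear diary entry suffices. With an assumed 2–5% relapse per 12-hour entry and 20% vs 10% dropout, the error is 3.5–4.7%. Requiring a 48-hour run brings it to about 2.6–2.7%.

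**The case against.** The rule is deliberate and disclosed: the Note in SAP 5.2.1 gives its reason, and with equal dropout it is conservative. The harm needs subjects to resolve and then leave, and the protocol works against that. Protocol 7.1.2 stresses finishing all visits after the illness has resolved, 7.1.3 ties total payment to completion through Day 14, and 8.5.4 keeps subjects who stop the device in the study. Withdrawals for baseline laboratory results come around Day 3 (Protocol 6.3), where the rule costs little. Protocol 4.1 reports no discontinuations in the earlier trial. All of this stands, and it makes the late-dropout column the least likely one.

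Two stronger readings are tempting. A reader might infer that the primary test has an inflated type I error. The documents do not support this: inflation needs more dropout on sham, which nothing in this double-blind, sham-controlled plan predicts, and the opposite imbalance makes the test conservative. A reader might also infer that the SAP's power arithmetic is wrong or that the primary analysis is underpowered. The mFAS arithmetic reproduces; it is the match to the censoring rule that fails. The FAS statement gives no dropout rate that the simulations could contradict.

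It is also fair that SAP 3.1 reports the enrolment increase as already made, so a restated power changes no decision. By-subject listings (16.2.1, 16.2.6.1, 16.2.6.3) would allow the counts by arm to be derived, and PP gives indirect information. None of this supplies an FAS analysis that tests the rule.

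**Conclusion.** The concern holds in this limited form and should be fixed. SAP 5.2.1 keeps resolved discontinuers at risk with no possible event, and no FAS analysis varies that. Equal dropout dilutes the hazard ratio and costs power. Unequal dropout biases in either direction, but that is a risk and not a prediction.

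The one stated figure not delivered under the SAP's own rule is the mFAS power at the 20% ceiling: about 68–90% with sham at 75%, or 74–84% with RD-X19 at 85%, where lost events explain part of the fall. The mFAS is a supportive population. With sham at 75%, at least 90% survives in all timings simulated at 5% dropout, and in only some at 10%. With RD-X19 at 85% it is only 88–90% even at 5%. Exact values rest on exponential times and assumed dropout timing. The direction was the same in every event-time model tried.

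**What to change.** Keep the primary rule.

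(a) Before unblinding, add to SAP 5.5.1 an FAS, Final Cohort sensitivity analysis for both primary endpoints. A non-hospitalised discontinuer who has met the success criterion continuously for a pre-specified minimum run (for example 48 hours, four diary entries) up to the last diary entry is an event at the start of that run. Other non-hospitalised discontinuers are censored at their last assessment. State that this relaxes maintenance to Day 14 and that its type I error is near nominal only if relapse is limited.

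(b) In SAP 3.3, replace the mFAS figure with the range under the censoring rule used, with its assumptions. With sham at 75%: 92–95% at 5% dropout, 85–94% at 10%, 68–90% at 20%. With RD-X19 at 85%: 88–90%, 84–88% and 74–84%.

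(c) Report, by Final Cohort arm, how many subjects discontinued during an open resolved run. The Table 14.1.1 shell pools sham, and Table 14.2.1.1 shows only the number censored. Align the last-assessment wording in 5.2.1 with the time-of-discontinuation wording in the footnotes to Tables 14.2.1.1 to 14.2.1.4.

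The cost is one sensitivity analysis for each endpoint, one added row, edited footnotes and a less favourable mFAS power statement. No extra patients are needed.

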- Review all pre-study medications, vitamins, supplements, and therapies up to 14 days prior to the start of screening that could impact the use of, or response to, the device and record on the appropriate source document. The use of any medications to treat some of the COVID-19-related symptoms (e.g., analgesics, antipyretics) should be recorded and the name of medication, dose, dosage form, and date and time(s) of administration should be reported. Antibiotics are not indicated as a treatment for COVID-19 and prior use of antibiotics (e.g. tetracycline, azithromycin) should be documented accordingly. Subjects receiving antibiotics for treatment of COVID-19 must discontinue use prior to study enrollment and this information should be documented. Subjects should be informed not to take antibiotics or other medications purported to treat COVID-19 (such as hydroxychloroquine or ivermectin) during their participation in the study. Antibiotic treatment of a bacterial infection during screening is a protocol exclusion because of the existence of an active concurrent disease. During the study, the decision to prescribe antibiotics is a clinical decision that should be made by the subject's primary care provider outside of the protocol. Such use, and the reason for such use, will be documented. While actively participating in the study, if antibiotics or other putative COVID-19 treatment drugs are

prescribed for treatment of COVID-19, volunteers must not use these drugs if they desire to remain in the active protocol. Subjects presenting at baseline with a fever of 100.5 or higher as measured via oral temperature will be advised to take acetaminophen for use in accordance with its labeling instructions. There is no prohibition on the use of analgesics for symptomatic treatment of pain. Any such use should be recorded on the concomitant medication form along with reason for use.

- Measure oxygen saturation via pulse oximeter
- Measure vital signs (HR, BP, RR, and oral temperature) and height and weight for determination of BMI.
- Perform full physical examination which will include assessments of the following organs and organ systems: skin, head, ears, eyes, nose, and throat (HEENT), neck, lungs, heart, liver, spleen, abdomen, extremities, lymph nodes (axillary and cervical), and nervous system.
- Obtain blood and urine for clinical screening laboratory evaluations:
 - Comprehensive Metabolic Panel (fasting or non-fasting)
 - CBC with differential

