#### 5.5.1 Analysis of Primary Efficacy Endpoint

The primary analysis for each of the two primary endpoints will be the comparison via an unstratified log-rank test between the RD-X19 treatment arm and sham from the Final Cohort and is based on the FAS population. This analysis will be supplemented with a graphical display and medians derived by the Kaplan Meier method.

All time-to-event analyses will be measured starting from the time of randomization. The data handling rules as described in Section 5.2.1 will be applied before analyses of the primary efficacy endpoints. These data handling rules cover cases related to subjects discontinuing the study early due to hospitalization for COVID-19, and cases related to subjects discontinuing the study early due to other reasons. Subjects that did not discontinue early but who did not achieve sustained resolution will be censored at the date of their Visit 5.

The Kaplan-Meier derived medians will be presented from the FAS population for the Final Cohort together with 95% CIs using the Brookmeyer & Crowley (1982) method and will include values for the RD-X19 treatment arm and the Sham arm. 25th and 75th percentiles will also be provided together with their 95% CIs using this same method.

Cox proportional hazards regression models (with a single term for treatment) will be employed to analyze the primary efficacy endpoints to derive a hazard ratio in each case between the RD-X19 treatment arm and the sham arm from the Final Cohort and will be based on the FAS population. Two-sided 95% confidence intervals and two-sided 90% confidence intervals will also be derived for the hazard ratios from the above models.

In addition, to evaluate the potential impact of subject baseline characteristics to the treatment effect estimation, the Cox proportional hazards regression will be performed for the Final Cohort based on the FAS population adjusting for the following set of covariates:

- 1) the COVID-19 Composite Severity Score at baseline defined as the sum of the eight individual COVID-19 signs and symptoms severity scores divided by eight (grouping of <1.25,  $\geq 1.25$ )
- 2) baseline disease status of mild vs. moderate disease (subjects meeting entry criteria are considered to be mild unless the physical/vital signs examination documents clinical signs suggestive of moderate illness)  
All subjects are designated as Mild with the exception of subjects:

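### SAP 5.2.1 holds COVID-19 admissions as failures to 384 h but censors death without COVID-19 admission, and study withdrawal for worsening COVID-19, at the last assessment

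*SAP*

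**What the plan says.** SAP 5.2.1 gives two rules for subjects who leave before Day 14.

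- Admission for COVID-19: "subjects who were hospitalized due to COVID-19 will be designated as treatment failures", with censoring at 384 h, the end of the Visit 5 window. They stay in the risk set throughout.
- All other exits: "For subjects who discontinued the study early for any reason other than hospitalization for COVID-19", diary data are used only up to the discontinuation date, and "such subjects will be considered censored at the time of their last assessment". They leave the risk set at that time.

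A Note in the same section adds: "Subjects discontinuing for any reason are ineligible to meet the success criteria on either primary efficacy endpoint". It sets no censoring time.

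The footnotes to Tables 14.2.1.1 to 14.2.1.4 repeat the split, though the Table 14.2.1.1 footnote dates the censoring differently: "Subjects discontinued for other reasons are censored at their time of discontinuation". SAP 5.5.1 deals with those who stay: "Subjects that did not discontinue early but who did not achieve sustained resolution will be censored at the date of their Visit 5".

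The primary test is an unstratified log-rank test in the FAS of the Final Cohort. Death appears in SAP 3.2 only as a component of the secondary severe-outcome endpoint. The mFAS, per-protocol, covariate-adjusted and pooled analyses all use the same censoring.

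**The concern.** Log-rank, Kaplan-Meier and Cox methods treat a censored subject as having the same later chance of resolution as those still at risk in that arm. That is not credible for someone who has died, or who left because the illness was getting worse. The SAP already takes this view for COVID-19 admissions, which is why they are held to 384 h. Two subjects with equally bad courses are therefore handled differently according to whether one was admitted.

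Removing non-resolvers from an arm's risk set raises that arm's apparent resolution rate. If RD-X19 loses more of them, harm is partly hidden. If sham loses more, benefit is understated. No planned analysis would show either.

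**Working it through.** **The plan's own figure first.** SAP 3.3 states at least 90% power in the mFAS (60:30, HR 0.4, one-sided α 0.025, up to 20% dropout, events 85% and 75%).

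- Events = (60 × 0.85 + 30 × 0.75) × (1 − 0.20) = 73.5 × 0.80 = 58.8.
- Schoenfeld: z = √(58.8 × 2/3 × 1/3) × |ln 0.4| − 1.96 = 3.615 × 0.916 − 1.96 = 1.35, so power is 0.912.

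The figure reproduces. The point does not rest on a sample-size error.

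**Direction of the hazard ratio.** The SAP code takes sham as reference and resolution as the event. Below, HR is RD-X19 over sham, and above 1 favours RD-X19.

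**Inputs from the documents.** 120:60 (Final Cohort of up to 180, 2:1); 85% of sham resolved by Day 14 (FAS assumption, SAP 3.3); one-sided α 0.025, for one endpoint without the Hochberg step; diary twice daily.

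**Assumed inputs.** The documents give no rate of death or withdrawal for worsening, so exit rates are varied. Exits are uniform over 48 to 240 h, and these subjects do not resolve by Day 14. Times are exponential. The HR of 1.5 in other subjects is also assumed. It lies between 1.21, which SAP 3.3's 90% and 85% imply under proportional hazards (ln 0.10 / ln 0.15), and 2, the inverse of its stated 0.5.

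**Mechanism by hand (10% RD-X19 exits, none on sham, no other effect).**

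- Resolution hazard: −ln(0.15)/336 h = 0.00565 per hour.
- RD-X19 has 12 exits and 108 other subjects. At the start, the ratio of apparent hazards is 108/120 = 0.90 under either rule.
- At 240 h the unresolved fraction of the others is exp(−0.00565 × 240) = 0.258, so 108 × 0.258 = 27.9 remain.
- SAP rule: all 12 have gone, so the ratio is 27.9/27.9 = 1.00.
- 384 h rule: all 12 are still counted, so the ratio is 27.9/(27.9 + 12) = 0.70.

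**Simulation of the whole follow-up.** Log-rank test and score-based HR, exp[(O − E)/V]. Repeat runs differ by about 0.01 to 0.03 in HR.

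| HR in others | Exits RD-X19 / sham | HR, SAP rule | HR, 384 h rule | Significant, SAP vs 384 h |
|---|---|---|---|---|
| 1 | 5% / 5% | 1.00 | 1.00 | 2.4% vs 2.4% |
| 1 | 10% / 0% | 0.90 | 0.79 | 0.8% vs 0.1% |
| 1 | 0% / 5% | 1.05 | 1.11 | 4.6% vs 9.2% |
| 1.5 | 1% / 1% | 1.49 | 1.48 | 66% vs 65% |
| 1.5 | 3% / 1% | 1.45 | 1.38 | 60% vs 49% |
| 1.5 | 5% / 5% | 1.48 | 1.42 | 62% vs 54% |
| 1.5 | 15% / 5% | 1.29 | 1.09 | 28% vs 6% |
| 1.5 | 5% / 15% | 1.62 | 1.70 | 80% vs 88% |

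The 15% rows show a limit and are not a forecast. The 1% and 3% rows are nearer what this population suggests.

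**The case against.** The strongest case against is that hardly anyone would fall under the disputed rule. Subjects are aged 18 to 65 and severe disease is excluded. The Protocol's Executive Summary reports no discontinuations in the earlier trial, EB-P12-01. Protocol 8.5.4 says that stopping the device is not leaving the study. Protocol 9.2 expects subjects seen in urgent care or an emergency room but not admitted to keep attending visits; their diaries then show non-resolution and they are censored at Visit 5. All of this stands. What remains is death without COVID-19 admission and full study withdrawal.

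It can also be said that holding leavers to 384 h defines a different, composite estimand. That stands for ordinary withdrawals, so the all-discontinuer version belongs in a sensitivity analysis. It has less force for death and worsening, because the SAP already uses that estimand for admission.

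A reader might infer more than the documents support:

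- That taking another COVID-19 drug forces early censoring. Protocol 9.1.1 says "volunteers must not use these drugs if they desire to remain in the active protocol", but this need not mean study exit. SAP Section 4 treats prohibited medication as a major deviation for the per-protocol set, so such subjects can remain in the FAS.
- That up to 20% of subjects are affected. SAP 3.3 gives that ceiling for discontinuations and hospitalisations of all kinds together, in the mFAS calculation.
- That the Note contradicts the censoring rule. Censoring already gives no event, and the Note sets no time.
- That balanced exits never matter. This holds only with no treatment effect; at HR 1.5 with 5% in each arm the two rules differ.

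**Conclusion.** The concern holds, within limits. The SAP handles equally bad outcomes differently according to COVID-19 admission, and gives death no rule for the primary endpoint. Measured against the failure convention that the SAP itself uses for admissions, unbalanced exits distort the HR in either direction: about 0.90 instead of 0.79 at 10% against 0%, and about 1.45 instead of 1.38 at 3% against 1%. With balanced exits and no effect, type I error is intact under both rules.

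The sizes rest on assumed exit rates and timing, on exponential times, and on these subjects not resolving by Day 14. Since few such exits are likely, the real effect is probably small. The change should be made, but the trial does not stand or fall on it.

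**What to change.** In SAP 5.2.1, apply the 384 h failure rule in the primary derivation to death from any cause and to study discontinuation documented as due to worsening COVID-19. Classify these reasons blind before database lock. Add one sensitivity analysis holding all early discontinuers to 384 h; it needs no classification. Bring the table footnotes into line, and use one censoring time (last assessment or discontinuation) for the exits that remain censored.

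Costs:

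- Protocol 8.5.3 has the reason recorded on the e-CRF, but the Table 14.1.1 shell has no category for death or COVID-19 worsening. Such cases would sit under adverse event, withdrawal by subject or other, so they need individual blinded review and two added rows.
- Power falls when there is a true effect, even with balanced exits: from about 62% to 54% at HR 1.5 with 5% exits in each arm, and by about two points or less at 1%.
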